3.1.1.2 Non-hematologic exceptions

- Transient (< 24 hours) grade 3 hypoalbuminemia, hypokalemia, hypomagnesemia, hyponatremia or hypophosphatemia which responds to medical intervention.
- Non-sustained (< 7 days) grade 3 liver function test (ATL, AST, alkaline phosphatase, total or direct bilirubin) abnormalities in the absence of clinical signs of hepatic dysfunction (lethargy, confusion, anorexia, pruritus, tremor); for patients with baseline grade 1 elevations, any increase $\geq 10 \times$ baseline will be considered dose-limiting and these patients will be closely monitored for liver function abnormalities.
- Grade 3 rash (maculo-papular, acneiform, or urticaria); if the rate of grade 3 rashes exceeds the expected rate (10% per mogamulizumab package insert) this will be reported as an unanticipated problem.
- First grade 3 infusion reaction associated with mogamulizumab administration (occurring within 24 hours of the dose).

Management and dose modifications associated with the above adverse events are outlined in Section 3.3. If a DLT is possibly, probably, or definitely related to IL-15 and unrelated or

Abbreviated Title: IL-15+Mogamulizumab

Version Date: 11/16/2020

unlikely to be related to mogamulizumab, patient may continue treatment with mogamulizumab alone if PI or designate deems it to be in the patient's best interest. Any DLT at least possibly related to mogamulizumab will lead to permanent discontinuation of protocol therapy regardless of attribution to IL-15. The same management will apply to an occurrence of any DLT-defining toxicity after the first 28 days of treatment; however, that toxicity will not be deemed a DLT for purposes of dose escalation.

3.1.2 Dose Escalation

Dose escalation will proceed according to the following schedule (**Table 6**). Dose escalation will follow the following guidelines (**Table 7**). DLT is defined above. Each patient will continue treatment at the dose level they were enrolled – there will be no intra-patient dose escalation.

The MTD is the dose level at which no more than 1 of up to 6 patients experience DLT during the DLT evaluation window(s), or the dose below that at which at least 2 (of ≤ 6) patients have DLT. The protocol will be amended to note the MTD once determined.

Table 6: IL-15 Dose Escalation Schedule

Dose Level	rhIL-15 (mcg/kg)	Mogamulizumab (mg/kg)
Level 1	2	1
Level 2	4	1

*Doses are stated as exact dose in units (e.g., mg/m², mcg/kg, etc.) rather than as a percentage.

Table 7: Dose Escalation Guidelines

Number of Patients with DLT at a Given Dose Level	Escalation Decision Rule
0 out of 3	Enter 3 patients at the next dose level.
≥ 2	Dose escalation will be stopped. This dose level will be declared the maximally administered dose (highest dose administered). Three (3) additional patients will be entered at the next lowest dose level if only 3 patients were treated previously at that dose.
1 out of 3	Enter at least 3 more patients at this dose level. 
 • If 0 of these 3 patients experience DLT, proceed to the next dose level. • If 1 or more of this group suffer DLT, then dose escalation is stopped, and this dose is declared the maximally administered dose. Three (3) additional patients will be entered at the next lowest dose level if only 3 patients were treated previously at that dose.
≤ 1 out of 6 at highest dose level below the maximally administered dose	This is generally the recommended phase 2 dose. At least 6 patients must be entered at the recommended phase 2 dose.

Abbreviated Title: IL-15+Mogamulizumab

Version Date: 11/16/2020

3.2 DRUG ADMINISTRATION

Each cycle is 28 days (4 weeks). The minimum window between initiation of new cycles is 26 days; a cycle delay due to scheduling or other administrative reasons (i.e., reasons other than toxicity/dose management as defined below) is 7 days.

Treatment will be administered on an inpatient basis during week 1 of the first cycle, and as outpatient during subsequent weeks and cycles unless decided otherwise by the principal investigator based on clinical judgment. Reported adverse events and potential risks are described in Section 14. Appropriate dose modifications are described in Section 3.3. No investigational or commercial agents or therapies other than those described below may be administered with the intent to treat the patient's malignancy. See **Table 8** below for description of drug regimen.

Table 8: Drug Regimen

Agent	Premedication; Precautions	Dose	Route	Schedule
rhIL-15	Premedicate with acetaminophen and/or ibuprofen	** in *** mL D5W with 0.1% HSA	IV over 24 hours	Days 1-5
Mogamulizumab	Premedicate with acetaminophen and an antihistamine*	1 mg/kg in **** mL 0.9% Sodium Chloride for Injection	IV over 1 hour	Days 1, 8, 15 and 22 of Cycle 1 and Days 1 and 15 of Cycles 2-6

* Mandatory for the first infusion; subsequently based on clinical judgement
 ** Doses as appropriate for assigned dose level
 *** Infusion volume of rhIL-15 per calculation in **APPENDIX D**
 **** Infusion volume of mogamulizumab titrated to a final concentration of the diluted solution between 0.1 mg/mL and 3.0 mg/mL

For a full detailed product description and administration guidelines, see Section 14. Infusions will be done via midline catheter. When administered on an outpatient basis, rhIL-15 will be infused via an ambulatory infusion pump.

3.2.1 Prophylactic and supportive care for IL-15

Patients will be given acetaminophen 500-650mg IV or orally, 30-60 minutes prior to each IL-15 infusion as first line, and ibuprofen 400 or 600mg orally, depending on reactions with acetaminophen as premedication.

3.2.2 Prophylactic and supportive care for mogamulizumab

In order to mitigate infusion related reactions, a premedication with an antihistamine and with acetaminophen 30 to 60 minutes prior to the first infusion of mogamulizumab is mandatory (e.g., 25-50 mg diphenhydramine and 500-650 mg acetaminophen IV or orally). Premedication should be administered for subsequent mogamulizumab infusions based upon clinical judgment and presence/severity of prior infusion reactions.

Abbreviated Title: IL-15+Mogamulizumab

Version Date: 11/16/2020

3.2.3 Other modalities or procedures

Patients will be observed in the day hospital or the inpatient unit for at least 30 minutes after administration of mogamulizumab for potential infusion-related reactions.

3.2.4 Delays in Dosing

During the first treatment cycle, mogamulizumab should be administered beginning on Day 1 and within +/- 1 day of the other scheduled visits (i.e., Days 8, 15 and 22). For subsequent cycles, mogamulizumab should be administered within +/- 2 days of the scheduled visits.

3.3 DOSE MODIFICATIONS

3.3.1 rhIL-15-specific Adverse Events

Please refer to the Comprehensive Adverse Event and Potential Risk list (CAEPR) for rhIL-15 presented in Section [14.1.2](#).

Dose of rhIL-15 is based on the dose level and patient's weight at the beginning of each cycle, and can only be modified for rounding and/or consistency with prior cycles, and not for adverse events or renal/hepatic dysfunction. Infusion may continue during correction of electrolyte and other laboratory abnormalities listed in Section [3.1.1](#). Infusion may be interrupted for up to two hours each day, but treatment should end 120 (± 1) hours after initiation on Day 1.

Abbreviated Title: IL-15+Mogamulizumab

Version Date: 11/16/2020

3.3.2 Mogamulizumab-specific Adverse Events

3.3.2.1 Treatment modifications for symptoms of infusion-related reactions

Table 9: Treatment modifications for infusion-related reactions

NCI-CTCAE Grade	Treatment Modification for Mogamulizumab
Grade 1-3 – mild, moderate, or severe Grade 1: Mild transient reaction; infusion interruption not indicated; intervention not indicated. Grade 2: Therapy or infusion interruption indicated but responds promptly to symptomatic treatment (for example, antihistamines, NSAIDs, narcotics, IV fluids); prophylactic medications indicated for ≤ 24 h. Grade 3: Prolonged (for example, not rapidly responsive to symptomatic medication and/or brief interruption of infusion); recurrence of symptoms following initial improvement; hospitalization indicated for clinical sequelae.	Temporarily interrupt the infusion of mogamulizumab and treat symptoms. Reduce the infusion rate by at least 50% when restarting the infusion after symptoms resolve. If reaction recurs and is unmanageable, discontinue infusion.
Grade 4 –life-threatening Life-threatening consequences; urgent intervention indicated.	Stop mogamulizumab infusion immediately and disconnect infusion tubing from the subject. Subjects have to be withdrawn immediately from study treatment and must not receive any further mogamulizumab treatment.
NOTE: If mogamulizumab infusion rate has been decreased by 50% or interrupted due to an infusion reaction, it must remain decreased for the next scheduled infusion. If no infusion reaction is observed in the next scheduled infusion, the infusion rate may be returned to baseline at the subsequent infusions	

IV = intravenous; NCI-CTCAE = National Cancer Institute-Common Terminology Criteria for Adverse Event; NSAIDs = nonsteroidal anti-inflammatory drugs

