3.1 STUDY DESIGN

In patients with relapsed/refractory MF/SS or ATLL, IL-15 will be administered by continuous intravenous infusion in a dose-escalation 3 + 3 system with a starting dose of 2 mcg/kg/day and a second dose level of 4 mcg/kg/day on days 1-5 of each of six cycles. Mogamulizumab will be

Abbreviated Title: IL-15+Mogamulizumab

Version Date: 11/16/2020

administered IV over at least 1 hour at a dose of 1 mg/kg on days 1, 8, 15 and 22 of cycle 1, and days 1 and 15 of each subsequent cycle. Treatment will continue for a maximum of 6 cycles or until toxicity (i.e., dose limiting toxicity as found in Section 3.1.1 or toxicity requiring hold as defined in Section 3.3) or progressive disease.

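### Table 9 restarts mogamulizumab after any Grade 1-3 infusion reaction, but under Section 3.1.1.2 a second Grade 3 reaction ends protocol therapy

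*Combined protocol and SAP*

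**What the plan says.** Section 3.1.1 makes any related Grade 3 to 5 toxicity in the first 28 days a DLT unless it is listed as an exception. The relevant exception in Section 3.1.1.2 reads "First grade 3 infusion reaction associated with mogamulizumab administration (occurring within 24 hours of the dose". The same section then states the consequence: "Any DLT at least possibly related to mogamulizumab will lead to permanent discontinuation of protocol therapy regardless of attribution to IL-15". It carries the rule past the DLT window: "The same management will apply to an occurrence of any DLT-defining toxicity after the first 28 days of treatment". Section 3.1 stops treatment for "dose limiting toxicity as found in Section 3.1.1 or toxicity requiring hold as defined in Section 3.3", and Section 3.9.1 lists the Section 3.1.1 toxicities among the reasons for removal from protocol therapy.

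Table 9 in Section 3.3.2.1 has one row for Grades 1 to 3. Staff interrupt the infusion and treat symptoms, and are then told: "Reduce the infusion rate by at least 50% when restarting the infusion after symptoms resolve". The only stop in that row is "If reaction recurs and is unmanageable, discontinue infusion". The table's note keeps the slower rate for the next scheduled infusion and allows a return to the usual rate after that if no reaction occurs. Withdrawal appears only in the Grade 4 row: "Subjects have to be withdrawn immediately from study treatment and must not receive any further mogamulizumab treatment".

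**The concern.** The word First in the exception matters. A second Grade 3 mogamulizumab infusion reaction is not exempt, so it is DLT-defining and, if at least possibly related to mogamulizumab, ends protocol therapy. Table 9 does not separate a first Grade 3 reaction from a second. It tells staff to restart more slowly, provides for a next dose, and does not refer back to Section 3.1.1.2.

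What is at stake is re-exposure of a patient who should be off protocol therapy. The restart decision is made on the day of the reaction, before the weekly team meeting. Infusion reactions are among the particular risks of the combination named in Section 12.4.1, so the table should be right for this event.

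**Working it through.** **Step 1: compare the rules, event by event.**

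| Mogamulizumab infusion reaction | Sections 3.1.1 and 3.1.1.2 | Table 9 | Agree? |
|---|---|---|---|
| Grade 1-2 | Not DLT-defining | Interrupt, restart slower | Yes |
| First Grade 3, within 24 hours of the dose | Exempt | Interrupt, restart slower | Yes |
| Second Grade 3, at least possibly related to mogamulizumab | DLT-defining; permanent discontinuation in any cycle | Interrupt, restart slower; stop that infusion only if a recurrence is unmanageable; next infusion at the reduced rate | No |
| Grade 4 | DLT-defining; permanent discontinuation | Withdrawal | Yes |

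The conflict is confined to the third line.

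**Step 2: bound the exposure if Table 9 alone were followed.** The plan gives no figure to reproduce. Inputs:
- Mogamulizumab on days 1, 8, 15 and 22 of cycle 1 and days 1 and 15 of cycles 2-6 (Section 3.1).
- Windows of 1 day either side for days 8, 15 and 22 of cycle 1, and 2 days either side in later cycles (Section 3.2.4).
- At least 26 days between cycle starts (Section 3.2), so the earliest cycle 2 day 1 is study day 1 + 26 = 27.
- Team meetings at least once weekly (Section 7.4.1), taken here as at most 7 days apart. This is an assumption.

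Shortest gap = earliest day of the later infusion minus latest day of the infusion with the reaction.

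| Second reaction at | Shortest gap to next infusion (days) | Shortest gap to the one after (days) |
|---|---|---|
| Cycle 1 day 8 | 14 - 9 = 5 | 21 - 9 = 12 |
| Cycle 1 day 15 | 21 - 16 = 5 | 27 - 16 = 11 |
| Cycle 1 day 22 | 27 - 23 = 4 | (27 + 14 - 2) - 23 = 16 |
| Cycles 2-6 day 1 | 14 - 2 - 2 = 10 | not needed |
| Cycles 2-6 day 15 | 27 - 17 = 10 | not needed |

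In cycle 1 the next infusion can fall inside 7 days (4 or 5), but the one after cannot (11 or more), so at most 1 precedes a meeting. In cycles 2-6 the next infusion is at least 10 days away, so 0 precede it.

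If the sponsor decided that a recurrence within one infusion is a second reaction, the earliest case would be cycle 1 day 1. The gaps are then 7 - 1 = 6 and 14 - 1 = 13 days, and the bound of 1 is unchanged.

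**Step 3: other checks.** Three provisions can act before the meeting: pre-dose assessments before every mogamulizumab dose (Section 3.5), the principal investigator's review of each patient's adverse events (Section 7.4.1), and 24-hour reporting when the reaction is serious (Section 8.3). The result of 0 to 1 is therefore an upper bound, not an expected exposure.

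**The case against.** The strongest reply is that this is a missing cross-reference. Directly after its list of exceptions, Section 3.1.1.2 sends the reader to Section 3.3 for management of those events. On that reading, Table 9 handles the exempt first reaction at the level of the infusion, while Sections 3.1, 3.1.1.2 and 3.9.1 decide whether the patient stays on therapy. Relatedness is judged by the principal investigator or designee, so Table 9 does not set DLT status. Nothing in the protocol says staff use the table alone.

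Much of this stands: the governing rule is clear, the harm depends on the table being read in isolation, and other checks exist. It does not remove the conflict. Table 9 is not limited to exempt events, because it covers Grade 4. It is not limited to acute handling, because its note governs later infusions and its Grade 4 row ends treatment. Its Grade 3 instruction is not restricted to a first occurrence. Table 10, beside it, does state when protocol therapy stops permanently, so a reader may expect the same of Table 9.

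A second objection is that any fix should not decide what counts as a second reaction. That is correct. Table 9's Grade 3 description includes "recurrence of symptoms following initial improvement", and a reader might infer that a recurrence on restarting belongs to the same reaction. Section 3.1.1.2 does not say so. Settling it would decide whether a same-infusion recurrence in cycle 1 is a DLT, which is a clinical decision for the sponsor.

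**Conclusion.** Table 9 and Section 3.1.1.2 give conflicting instructions for one event: a second Grade 3 infusion reaction at least possibly related to mogamulizumab. Section 3.1.1.2 governs, and Table 9 should be corrected to match it. This is a low-severity safety consistency correction.

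The exposure is at most the remainder of the restarted infusion plus 0 to 1 further infusions before the weekly review. This rests on meetings no more than 7 days apart and on the team recognising the event at the first meeting after it. The documents give no rate of second Grade 3 reactions.

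Three stronger readings are not supported:
- A reader might infer that the protocol allows treatment to continue after a second Grade 3 reaction. Sections 3.1, 3.1.1.2 and 3.9.1 say otherwise.
- A reader might infer that dose escalation is compromised. DLT counting is fixed by Section 3.1.1, and Table 9 does not alter it.
- A reader might infer that a patient could go on to receive all remaining infusions. That would need those three sections and every pre-dose, adverse event and weekly review to be overlooked at each later dose.

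**What to change.** Split the Grade 1-3 row of Table 9 in two:
- **Grades 1-2 and a first Grade 3 reaction:** keep the present instruction to interrupt, treat and restart more slowly.
- **A second Grade 3 reaction, in any cycle, at least possibly related to mogamulizumab:** once it is graded 3, stop the infusion, do not restart it, and permanently discontinue protocol therapy per Section 3.1.1.2.

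The phrase once graded 3 is needed because one Grade 3 criterion may be met only after a restart. Do not add a definition of what belongs to the same reaction. The sponsor should decide separately whether a recurrence during one infusion counts as a second reaction, because that affects DLT counting.

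The cost is one edited table row. No procedures, visits or patients are added, and the governing rule does not change.

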3.3.2.2 Treatment modifications for dermatologic toxicity

Table 10: Treatment Modifications for Dermatological AEs

Dermatological irAEs		
Rash	Initial Management	Resuming protocol treatment
Grade 1 Covering $<10\%$ of body surface area	Continue protocol therapy Consider topical steroids	N/A
Grade 2 to 3 Covering $>10\%$ of body surface area	Hold protocol therapy Administer topical steroids for at least 2 weeks	Rash improves to Grade ≤ 1
Grade 4 Life-threatening consequences; Stevens-Jonson syndrome (SJS) or	Hold protocol therapy for suspected SJS/TEN Permanently discontinue protocol therapy if SJS/TEN has been	SJS/TEN has been excluded and the rash improves to Grade ≤ 1

Abbreviated Title: IL-15+Mogamulizumab

Version Date: 11/16/2020

Dermatological irAEs		
Rash	Initial Management	Resuming protocol treatment
toxic epidermal necrolysis (TEN)	confirmed or if there are life-threatening consequences	

3.4 STUDY INTERVENTION COMPLIANCE

Adherence to the protocol will be verified by reviewing the Medical Administration Record (MAR) section of the medical record, which will serve as source documentation.

3.5 ON STUDY EVALUATIONS

Prior to mogamulizumab administration (Days 1, 8, 15 and 22 of cycle 1 and days 1 and 15 of cycles 2-6), pre-dose assessments must be performed (up to 3 days prior). After Cycle 1, pre-dose assessments may be performed up to 3 days prior to a cycle except where otherwise noted. The results from all procedures/tests must be reviewed prior to initiation of each cycle of treatment for consideration of dose modifications and delay of therapy.

Treatment with rhIL-15 and mogamulizumab will continue for six cycles or until disease progression, unacceptable treatment-related toxicity or other reasons outlined in Section [3.9.1](#).

Refer to the Study Calendars (Section [3.7](#)) for a complete list of procedures to be performed at each scheduled study visit. See also Section [5.1](#) for all samples to be collected for correlative research. During treatment, it is expected that all laboratory and clinical assessments be conducted at the NIH (including post-treatment imaging evaluations); results from outside NIH will only be accepted at the discretion of the investigator.

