1.2.5.1 IL-15 in the Treatment of Patients with Metastatic Malignancy

Three clinical trials of rhIL15 have had their patient accrual completed with 19-29 patients each: one by bolus infusion over 30 minutes(37), one by subcutaneous (SC) administration(38), and the third by CIV of rhIL15 to patients with metastatic malignancy.(39) The MTD by bolus infusion was 0.3 mcg/kg/day, whereas the MTD with SC administration was 3 mcg/kg/day and by CIV was 2 mcg/kg/day.

In the phase I study of bolus infusions of recombinant Escherichia coli produced human IL-15, the MTD was determined to be 0.3 μ g/kg/day for 12 days. At a dose of 3 μ g/kg/day the patients developed fever and rigors and a reduction in blood pressure that were concurrent with a maximum of 50-fold elevations of circulating IL-6 and IFN γ concentrations. The bolus infusion of IL-15 at 3 μ g/kg/day led to a 10-fold expansion of NK cells. When IL-15 was administered subcutaneously 5 days a week for 2 weeks at 3 mcg/kg/day there was a significant increase (mean 10.8 fold) in the number of circulating NK cells. Furthermore, when it was administered at 2 mcg/kg/day by continuous intravenous infusion there was an 8-fold increase in this number during the infusion. Following termination of the infusion there was a 38-fold increase in the number of NK cells and a 358-fold increase in the number of CD56bright NK cells (Figure 2A). A trial of IL-15 by CIV for 5 days has been initiated, and in the 11 patients studied following treatment there was a 21 to 44-fold increase in the number of circulating NK cells, and up to an 8.9-fold increase in the number of CD8+ T cells (Figure 2B, Table 2 and Table 3).

Abbreviated Title: IL-15+Mogamulizumab

Version Date: 11/16/2020

[figure not shown]

Figure 2: Increase in lymphocytes, predominantly NK cell count, during continuous infusion of rhIL-15.

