3.7 STUDY CALENDAR

Procedure	Screening	Baseline	Study Cycles						Disease Evaluations	End of Treatment and Disease Progression	Post-Treatment Follow-Up		
			C1			C2-6					Safety ¹	Follow-Up (Prior to PD)	Survival (Post-PD)
Scheduling Window (Days):	-28 to -1 ²		-14 ³	8 (-3)	15 (-3)	22 (-3)	1 (-3)	15 (-3)	Every 8 weeks ⁴	Treatment discon/PD ⁵	Day 30 (±7)	Every 60 or 90 days ⁶	Every 6 months ⁷
Confirmation of Diagnosis ⁸	X												
Physical Exam and ECOG PS ⁹	X	X		X	X	X	X	X		X	X	X	
CBC with Differential	X	X	X	X	X	X	X	X		X	X	X	
Reticulocyte Count	X	X	X	X	X	X	X	X		X	X	X	
Chemistry Panels ¹⁰ , LDH	X	X	X	X	X	X	X	X		X	X	X	
Serum Lipase and Amylase		X	X	X	X	X	X	X		X	X	X	
Uric Acid, Total Protein		X	X	X	X	X	X	X					
PT/INR and aPTT	X	X	X				X			X	X	X	
Thyroid Function (i.e., TSH, T4)	X	X	X				X			X	X	X	
Urinalysis	X	X	X				X			X			
Pregnancy Test (urine/serum; WOCBP)	X	X	X										
Hepatitis B and C, HIV Antibody, HTLV-1/2	X												
HLA typing (A, B, C, DR, DQ)		X	X										
Anti-nuclear antibody (ANA), rheumatoid factor (RF) and anti-thyroid antibody	X	X											
Clonal T-cell receptor rearrangement by PCR	X												
Iron panels, Folate, and B12, C-reactive Protein, IL-2Ra		X	X										
Creatine phosphokinase (CPK), troponin	X	X	X							X		X	

Abbreviated Title: IL-15+Mogamulizumab
Version Date: 11/16/2020

Procedure	Screening	Baseline	Study Cycles						Disease Evaluations	End of Treatment and Disease Progression	Post-Treatment Follow-Up		
			C1			C2-6					Safety ¹	Follow-Up (Prior to PD)	Survival (Post-PD)
Scheduling Window (Days):	-28 to -1 ²		-14 ³	8 (-3)	15 (-3)	22 (-3)	1 (-3)	15 (-3)	Every 8 weeks ⁴	Treatment discon/PD ⁵	Day 30 (+7)	Every 60 or 90 days ⁶	Every 6 months ⁷
Pulmonary function tests (PFTs) ¹¹	X												
T, B, NK cell subsets		X		X	X		X	X		X	X	X	
Imaging studies ¹²	X	X							X	X		X	
MRI, Lumbar Puncture ¹³		X							X	X		X	
Bone Marrow Aspiration/Biopsy ¹⁴		X								X	X		
Flow Cytometry ¹⁵		X							X	X	X	X	
Clinical photography and dermatology assessment/ global score ¹⁶		X							X	X		X	
Radiologic Evaluation/ tumor measurement ¹⁷		X							X	X		X	
EKG, TTE	X												
Symptoms/Adverse Events Assessment, Concomitant Medication Review	X	X					X			X	X	X	
Research Blood/Tissue Samples ¹⁸		X	Refer to Section 5.1										
Survival Status													X

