5 CORRELATIVE STUDIES

5.1 SUMMARY

This study will attempt to use rhIL-15 to increase NK cell number and activity, thereby enhancing the ADCC of mogamulizumab in treatment of patients with relapsed and refractory MF/SS and ATLL. ADCC capacity of ex vivo PBMCs will be tested on CCR4-expressing cell lines before, during, and after protocol treatment. CCR4 mutation status will be determined for each patient by batch processing, and correlated with response and survival. Differences in circulating immune cell subsets associated with administration will be followed throughout treatment to both study the effects of combined rhIL-15/mogamulizumab therapy on the immune system, and to identify potential biomarkers that would be predictive of response. With the same goal in mind, immune cell subsets in the tumor microenvironment before and after treatment will be determined using single-cell RNA sequencing.

Sample	Collection Details*	Time Points							Supervising Laboratory/Investigator
		Baseline	C1 D8	C1 D15	C2-6 D1	C2-6 D15	Follow-up [#]		
Blood Samples									
Lymphocyte subset testing	• 2 x 10mL K ₂ EDTA (lavender-top) tubes	X	X	(X)	(X)	(X)	(X) ¹	Immunology section, NIH CC	
ADCC of mogamulizumab	• 3 x 10mL sodium heparin green-top tubes	(X) ²	(X) ²					[name]	
Tissue immune cell subsets (comparison)	• 1 x 5mL sodium heparin green-top tube	(X)		(X)			(X)	[name]	

Abbreviated Title: IL-15+Mogamulizumab**Version Date:** 11/16/2020

Sample	Collection Details*	Time Points						Supervising Laboratory/ Investigator
		Baseline	C1 D8	C1 D15	C2-6 D1	C2-6 D15	Follow-up [#]	
Circulating tumor DNA, plasma banking	• 1 x 10mL K ₂ EDTA tube • 1 x 10mL Streck/BCT tube	X	(X)	X	(X)	(X)	X ³	[name] (Leidos CSL)
PBMC banking	• 2 x 10mL sodium heparin green-top tubes	X	X	X	X	X	X	
Anti-IL-15 antibodies	• 1 x 4mL SST tube	X			X		X ¹	
CCR4 expression	• 2 x 10mL sodium heparin green-top tubes	(X)	(X)		(X)			[name] (Laboratory of Pathology)
CCR4 mutation status	• 2 x 10mL sodium heparin green-top tubes	(X)						
Tissue Samples								
CCR4 expression	• One core biopsy sample in formalin	X**		(X)				[name] (Laboratory of Pathology)
CCR4 mutation status	• One core biopsy sample in formalin	X**		(X)				[name] (Laboratory of Pathology)

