Tissue immune cell subsets	• Two core biopsy samples in RPMI 1640 with 10% human serum and antibiotics • One core biopsy sample in formalin NOTE: Samples may be tumor tissue or bone marrow aspirate/biopsy	X**		(X)			(X)	[name] (Laboratory of Pathology)
Single-cell RNA-Seq	• One core biopsy sample in RPMI 1640 with 10% human serum and antibiotics	(X)		(X)				[name] (Laboratory of Pathology) and CCR single cell core
Other Samples								
Germline DNA	• Blood, Buccal Swab, or Saliva (preferred)	X						[name] (Leidos CSL)

Abbreviated Title: IL-15+Mogamulizumab

Version Date: 11/16/2020

Sample	Collection Details*	Time Points						Supervising Laboratory/ Investigator		
		Baseline	C1 D8	C1 D15	C2-6 D1	C2-6 D15	Follow-up [#]			
(X) = Optional; samples will be collected if adequate time/staff available for processing. If an optional sample is not collected at baseline, it would also not be collected in follow-up unless specifically requested by the PI.										
*Tubes/media may be adjusted at the time of collection based upon materials available or to ensure the best samples are collected for planned analyses.										
** Tumor biopsy is required if archival tissue is not available or adequate; otherwise, this is optional										
#Subjects who discontinue treatment for a reason other than disease progression and who do not start new treatment should continue to have study bloods collected at the scheduled time points.										
¹ At the end of treatment only.										
² For ADCC of mogamulizumab, Baseline and C1D8 samples should be collected for at least one patient per dose level, and for at least three patients at the MTD										
³ At each follow-up visit prior to disease progression, as specified in Section 3.6.2 .										

Note: If there is an optional biopsy for research in the protocol, then the patient will consent at the time of the procedure. If the patient refuses the optional biopsy at that time, the refusal will be documented in the medical record and in the research record.

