10 STATISTICAL CONSIDERATIONS

10.1 STATISTICAL HYPOTHESIS

- Primary Endpoint(s):
 - Maximum tolerated dose (MTD) of rhIL-15 administered intravenously for 5 days in combination with mogamulizumab for up to 6 cycles
 - Frequency (number and percentage) of treatment-emergent AEs
- Secondary Endpoint(s):
 - Overall response rate (including CR and PR)

Abbreviated Title: IL-15+Mogamulizumab

Version Date: 11/16/2020

- ORR, TTP, and PFS by CCR4 mutation status (mutated versus wild type) and presenting diagnosis (MF/SS versus ATLL, MF versus SS, acute/chronic versus lymphoma subtype ATLL)
- Duration of response
- Progression-free, event-free, and overall survival
- Changes in percentage and absolute number of peripheral blood lymphocyte subsets
- Quantitation ADCC performed ex vivo on PBMCs obtained from the patients before and during treatment
- Characterization of changes in immune cell infiltrates of tumor deposits by immunohistochemical and molecular analysis of core biopsies obtained before and during treatment

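### The minus-3-day window on the cycle 1 Day 8 lymphocyte-subset draw spans the end of the rhIL-15 infusion, and the Section 5.1 Day 8 research samples have no stated window

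*Combined protocol and SAP*

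**What the plan says.** - **Window.** Section 3.5 requires assessments before each mogamulizumab dose and sets their timing: "pre-dose assessments must be performed (up to 3 days prior"). Day 8 of cycle 1 is among the listed doses. The Section 3.7 calendar heads that column Day 8 with minus 3 days.
- **What is measured in that column.** The calendar row "T, B, NK cell subsets" is marked at baseline, cycle 1 Days 8 and 15, Days 1 and 15 of cycles 2-6, end of treatment, the safety visit and follow-up.
- **Infusion.** Section 3.3.1: "treatment should end 120 (± 1) hours after initiation on Day 1".
- **Research samples.** In the Section 5.1 table, "Lymphocyte subset testing" is required only at baseline and C1 D8. Later time points carry the bracketed mark, defined as "X) = Optional; samples will be collected if adequate time/staff available for processing". C1 D8 is also the only on-treatment ADCC draw in that table, and PBMC banking is required there. The table gives no draw window, and the calendar's research row only points to Section 5.1.
- **Endpoint.** Section 10.1 lists among the secondary endpoints: "Changes in percentage and absolute number of peripheral blood lymphocyte subsets". Section 1.1.3 places lymphocyte subsets among the exploratory objectives. Ex vivo ADCC is secondary in both Section 1.1.2 and Section 10.1.
- **Background data.** For continuous infusion at 2 mcg/kg/day, Section 1.2.5.1 says "there was an 8-fold increase in this number during the infusion", and then: "Following termination of the infusion there was a 38-fold increase in the number of NK cells".

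**The concern.** A pre-dose window of a few days suits safety laboratory tests. Here the same window is applied to a pharmacodynamic measure at the one visit where it crosses the end of the infusion. NK number is the quantity rhIL-15 is meant to raise, and the protocol's background data suggest that it differs markedly during and after infusion. If some patients are sampled on Day 5 and others on Day 8, the Day 8 summary mixes two biological states.

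An early draw is realistic. Section 3.2 makes week 1 of cycle 1 inpatient, so the patient is on the unit on Day 5. Section 5.2.2.1 also anticipates that the immunology laboratory may be unable to run the panel on the specified days.

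At stake is the interpretability of the first post-treatment NK value in a trial with few patients per dose level. If the Section 5.1 tubes are drawn under the same window, the ADCC and banked PBMC samples labelled C1 D8 are affected too.

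**Working it through.** **1. When the infusion ends.** 120 h = 5 × 24 h, so an infusion started on Day 1 ends on Day 6 at about the same clock time. The ±1 h tolerance does not change the day-level result.

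**2. When the draw may fall.** Day 8 − 3 = Day 5, so the calendar allows Day 5 to Day 8.

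**3. Draw time relative to infusion end.** Hours from end = 24 × (draw day − 1) + draw clock hour − (start clock hour + 120). The documents give no clock times. Assumed: start at 08:00, 12:00 or 18:00; draw at 08:00 or 14:00.

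| Draw day | Hours from infusion end | State |
|---|---|---|
| 5 | −34 to −18 | during, in every case |
| 6 | −10 to +6 | either |
| 7 | +14 to +30 | after |
| 8 | +38 to +54 | after |

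Example, Day 5 at 14:00 with an 08:00 start: 96 + 14 − 128 = −18 h. Day 8 at 14:00 with the same start: 168 + 14 − 128 = +54 h.

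**4. Whether other columns share the problem.** Day 15 − 3 = Day 12, six days after the infusion ends. In cycles 2-6, Day 1 − 3 precedes that cycle's infusion, and Day 15 − 3 is again Day 12. Only the cycle 1 Day 8 window crosses the end of infusion.

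**5. Size of the contrast in the documents.** At 2 mcg/kg/day: 38 / 8 = 4.75. These are observed values with no inputs from which to re-derive them. For 5-day infusion, Section 1.2.5.1 gives only post-treatment values, 21- to 44-fold. Set against the 8-fold value from the other regimen, that is 21/8 = 2.6 to 44/8 = 5.5, a cross-trial range for illustration only.

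**6. What mixing would do, if 8 and 38 applied here.** Let f be the share of patients drawn during infusion (an assumption).

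- Apparent geometric mean = 8^f × 38^(1−f).
- Log-scale SD added by mixing = ln(4.75) × √(f(1−f)).

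| f | Geometric mean fold change | Added log SD |
|---|---|---|
| 0 | 38 | 0 |
| 0.25 | 25.7 | 0.67 |
| 0.5 | 17.4 | 0.78 |
| 1 | 8 | 0 |

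In a dose level of three patients, one early draw gives (8 × 38 × 38)^(1/3) = 22.6 instead of 38.

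**The case against.** **The window and the required-sample status come from different schedules.** The minus-3-day window belongs to Section 3.5 and the calendar. The rule that only baseline and C1 D8 are required belongs to Section 5.1, which states no window. A reader might infer that the plan permits its only mandatory on-treatment subset sample to be taken on Day 5. The documents do not support that. Under the calendar, the window applies, but subsets are also marked, without the optional bracket, at Day 15 and in later cycles. Under Section 5.1, later samples are optional, but whether the window applies is unstated. What stands is that the calendar's Day 8 subset row has a window crossing the end of infusion, and that Section 5.1 does nothing to prevent the same.

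**Draw time is recorded.** Section 5.2.2.1 requires date and time on the subset tubes, and Section 3.4 makes the administration record the source document. On- or post-infusion status can therefore be worked out, so the mixing is neither hidden nor beyond recovery. This largely stands. However, Sections 5.2.2.2 and 5.2.2.4 do not repeat the label rule for the ADCC and PBMC tubes, and nothing in Section 10.4 uses draw time. Knowing the time also does not turn a Day 5 value into a Day 8 one.

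**The 4.75 ratio is not for this regimen.** The reference-list title of the cited continuous-infusion trial says 10 days (240 hours). Section 1.2.5.1 does not say when during infusion, or how long after it, each value was seen. This objection stands in full.

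**Consequences are modest.** A reader might infer that timing could pass for a dose effect between 2 and 4 mcg/kg/day, or that it outweighs the 2-fold dose step. Section 10.4 plans no between-dose comparison of NK expansion, and a fold change in cell count is not on the same scale as a fold change in dose. Association of blood biomarkers with response is exploratory (Section 10.4.9). Appendix B describes ADCC testing on Day 15 cells whereas Section 5.1 lists C1 D8, so any effect on ADCC is conditional.

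**Day 4 is not needed.** Adding the ±1 day mogamulizumab window of Section 3.2.4 would reach Day 4, but that stacks two allowances beyond the calendar's stated limit. Day 5 is sufficient for the point.

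**Conclusion.** The point holds in limited form. A stated window, followed as written, allows the cycle 1 Day 8 subset sample to be taken 18 to 34 hours before the infusion ends or 38 to 54 hours after it (under the assumed clock times). The Section 5.1 C1 D8 samples have no window and no rule linking them to the end of infusion.

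The timing conclusion rests only on the stated window and infusion length. Its biological size does not: 4.75 is the best during-versus-after contrast in the documents, not a measurement for 5-day infusion with mogamulizumab. The share of patients who would be drawn early is unknown, so the mixing figures are scenarios.

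The effect is confined to the Day 8 value of the lymphocyte-subset endpoint and possibly ADCC. Later calendar subset samples and the MTD and DLT endpoints are unaffected. This is an inexpensive improvement, not a threat to the trial's primary result.

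**What to change.** 1. In the Section 3.7 calendar and the Section 5.1 table, require the cycle 1 Day 8 subset sample and the C1 D8 research samples to be drawn pre-dose on the day of the Day 8 mogamulizumab visit, and after the rhIL-15 infusion has ended.
2. Derive hours since end of infusion for each sample from the recorded draw time and the administration record. State the draw-time label rule for the ADCC and PBMC tubes as well.
3. Add a sentence to Section 10.4 saying how this interval is used: at minimum, report it with the Day 8 values and show any during-infusion samples separately.
4. Keep the minus-3-day window for safety laboratory tests.

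Cost: wording in the calendar, Section 5.1 and Section 10.4. The patient already attends for the Day 8 dose, so there is no extra visit or tube, and treatment is unchanged. The downside is slightly less scheduling flexibility for these samples.
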